Self-affirmation intervention for people newly diagnosed with advanced cancer:
A preliminary efficacy trial

NCT 05235750

March 27, 2024

Title: Self-affirmation intervention for people newly diagnosed with advanced cancer: A preliminary efficacy trial

PI: [name]

Study Title: Self-affirmation intervention for people newly diagnosed with advanced cancer: A preliminary efficacy trial

Principal Investigator: [name]
College of Integrated Clinical Enterprise SUSL Surgical Specialties
University of Arkansas for Medical Sciences
[name]
[name]

Email: [contact]

Study location: Winthrop P. Rockefeller Cancer Institute
[name]
[name]

Arkansas Hospice
[name]
[name]

Title: Self-affirmation intervention for people newly diagnosed with advanced cancer: A preliminary efficacy trial

PI: [name]

Hypothesis and/or Specific Aims or Objectives

The **primary aim** of this study is to explore the effects of self-affirmation via writing on patients newly diagnosed with advanced cancer, calculate effect sizes of the outcome variables, and estimate the appropriate sample size for the main study.

The **secondary aim** is to test the validity of the functional assessment of chronic illness therapy- spiritual well-being 12 item scale (FACIT-Sp-12), in its current (**Appendix A**) and revised forms (**Appendix B**).

It is hypothesized that: self-affirmation at the time following a diagnosis of an advanced cancer by affirming values or beliefs that are salient to self will help patients enhance self-esteem, reinforce spiritual well-being, decrease levels of anxiety or depression, and improve quality of life (QoL).

Study Design and Procedures

A single group time series study design will be employed (**Figure 1**).

[figure not shown]

Figure 1: Timeline for the four data collection points

The intervention Participants will be asked to write as guided by the researcher starting from Time 2 (two weeks post-baseline) for 4 weeks.

Specific criteria on the writing task:

- 1) write with a focus on affirming one's fundamental values and beliefs,
- 2) write in connection with one's cancer diagnosis, and
- 3) write at least once for a minimum of 20 minutes per week for four weeks.

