To ensure that participants understand the nature and essence of the intervention, each patient will receive a page of writing instructions and a brief educational/informational session with the principal investigator (PI), both of which occur at two weeks post-baseline (Time 2 or T2); the writing instructions clarify the key expectations for the participants with respect to the writing intervention (in line with the criteria above) followed by examples to address what self-affirmation writing is and is not for this intervention.

Title: Self-affirmation intervention for people newly diagnosed with advanced cancer: A preliminary efficacy trial

PI: [name]

Both an online portal and notebooks for drafting and submitting the writings will be created for participants; patients may choose either approach to perform the writing task. At the end of the study period (or any other point), participants have the option to share their writings with the PI. However, given the high privacy nature of the content, sharing writings with the researchers is not required (which will be clarified with the participants) in order to encourage writing without reservation.

Study Population

The targeted participants are adult patients (age 18 or older) newly diagnosed with advanced cancer, and the total number of subjects to be enrolled will be a minimum of 50. This sample size is chosen based on an estimated effect size of 0.4-0.5 to test differences between paired observations in one sample, with α 0.05 and power 0.80 (Cohen, 1988).

The sample size estimate is tentative given the exploratory nature of this pilot study as the actual attrition rate as well as effect size may not be accurately predicted due to the high variability as found in the literature (Bai, 2021).

Recruitment Strategy

Patient recruitment for this pilot study will take place at two study sites: the Winthrop P. Rockefeller Cancer Institute at the University of Arkansas for Medical Sciences (UAMS) and the Arkansas Hospice.

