The UAMS Winthrop P. Rockefeller Cancer Institute is Arkansas' only academic cancer treatment and research facility. The PI will work with a study coordinator or a research assistant who helps identify and, if possible, consent eligible patients into the study. Specifically, the PI will receive patient referrals directly from the study coordinator or the research assistant for enrollment, meet with the potential participants, verify their eligibility before inviting them to join the study. The PI may also work directly with collaborating clinicians and/or accessing the electronic medical records to facilitate the enrollment progress. A waiver of the HIPAA authorization requirement will be requested for study enrollment purposes that permits the PI accessing the electronic medical records to identify potential study participants and/or verify their eligibility.

The Arkansas Hospice is the state's largest, non-profit hospice organization dedicated to enhancing quality of life for those facing serious illness and loss. The collaborating clinicians at the Arkansas Hospice will help identify eligible research participants and then refer these potential patients to the PI. The PI will go to meet with the potential participants and verify their eligibility before obtaining informed consent and the subsequent data collections.

Title: Self-affirmation intervention for people newly diagnosed with advanced cancer: A preliminary efficacy trial

PI: [name]

The PI will closely monitor the recruitment progress weekly and adjust/modify the recruitment method as necessary or seek/develop alternative recruitment strategies to ensure that the study recruitment proceeds timely.

Inclusion Criteria

- 1) within 8 weeks of being informed of diagnosis (primary or recurrent)
- 2) cancer stage III or IV of a primary solid tumor, or a high-grade hematological malignancy, and
- 3) age 18 years or older

Exclusion Criteria

- 1) medical condition precluding participation (e.g., too ill or fatigued, acute mental confusion as determined by the treating physician), or
- 2) enrolled in other psychosocial experiments

Measures

Self-esteem

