In addition to the demographic information (**Appendix G**), as well as other health information (including medical conditions and cancer treatments) to be collected from the medical records, patients will be asked to rate the perceived threat (Parle et al., 1996) at the baseline whether and to what extent (on a 4-point scale) they viewed the cancer

Title: Self-affirmation intervention for people newly diagnosed with advanced cancer: A preliminary efficacy trial

PI: [name]

diagnosis as a threat. During each data collection meeting, participants will be asked to make global ratings of changes (GRC) (Jaeschke et al., 1989) in QoL and spiritual well-being on the five-point response categories (Cella et al., 2002) at the scale and factor levels.

Finally, it has been suggested that measuring the patients' assessment of the importance of different life quality domains over time is one way to gather possible changes in attitude and values, and aid interpretation of the outcome changes (Rustøen et al., 2000). The importance ratings for each subscale of the FACT-G and the FACIT-Sp-12 will be collected at each data-collection meeting.

Table 1 The schedule of administration of questionnaires

Questionnaires	Baseline (1 st meeting)	2 weeks post- baseline (2 nd meeting)	6 weeks post- baseline (3 rd meeting)	8 weeks post- baseline (4 th meeting)
Perceived threat	X			
RSES	X	X	X	X
FACIT-Sp-12*	X	X	X	X
HADS	X	X	X	X
FACT-G	X	X	X	X
Demographic Form	X			
Progress of the disease		X	X	X
Intervention implementation debriefing checklist**			X	X

FACIT-Sp-12, the 12-item Functional Assessment of Chronic illness Therapy-Spiritual Well-Being Scale; **FACT-G**, the Functional Assessment of Cancer Therapy-General; **HADS**, the Hospital Anxiety and Depression Scale; **RSES**, the Rosenberg Self-Esteem Scale.

*including the original scale and the revised items (Please refer to the enclosed measures for details)

**including the start time, duration, frequency and the focus/topic of the writing as well as the perceived helpfulness

Additionally, an exit survey (**Appendix H**) will be used to capture the number of eligible patients who decline or refuse participation, lost to follow-up at any point of study, as well as reasons of the lost to follow-up and/or withdrawal.

Note: data collections will occur at the above scheduled windows +/- 3 days.

Risks and Benefits

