Due to the exploratory nature of the pilot study, both the variables to be explored (that is, allowed to vary and without definitions) and the intervention parameters to be controlled (as specified above) will be collected in a checklist of the implementation of the intervention (Appendix F). Specifically, the participants' feedback on the start time, duration, frequency, the topic of the writing, helpfulness of the study as well as the potential improvement in design), will be requested along with their response to questions concerning the evidence of treatment implementation (including whether writing occurred, whether the minimum amount of writing duration/frequency, and the prescribed focus of the writing as well as the relevance to cancer diagnosis were met).

b. Explore the intervention effects, calculate effect sizes of the outcome variables, and estimate the appropriate sample size for the main study.

Mean changes in patients' self-esteem, spiritual well-being (at the scale and factor levels), anxiety and depressive symptoms as well as QOL (global, total score and each subscale) will be evaluated using regression models for longitudinal data (i.e., repeated measures analysis of variance). The importance ratings for each subscale of the FACT-G and the FACIT-Sp-12 will be collected during each data collection meeting to aid interpretation of the intervention effect. Perceived threat at baseline and disease progression at each follow-up data collection meeting will be analyzed as moderators for exploratory analysis; psychosocial counseling or other supportive therapy/service/treatment received will be included as covariates. SAS® software will be used to perform all the proposed analyses. For hypothesis testing, an alpha (α) of 0.05 will be selected.

The standardized mean difference (Cohen's d statistic), or effect size will be computed by dividing the mean change by the standard deviation (SD) at the baseline (Kazis et al., 1989). In addition, raw score changes from baseline to follow-up will be assessed to interpret the clinical significance of the change by comparing with the established estimates of the minimal clinically important difference (MCID) (Jaeschke et al., 1989) for

Title: Self-affirmation intervention for people newly diagnosed with advanced cancer: A preliminary efficacy trial

PI: [name]

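### Writing starts at Time 2, but raw FACT-G change is taken from the first visit and the visits behind Cohen's d are not named, so two weeks without writing can count as intervention effect

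*Combined protocol and SAP*

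**What the plan says.** **Design and timing.** Under Study Design and Procedures, "A single group time series study design will be employed". The intervention is set there too: "Participants will be asked to write as guided by the researcher starting from Time 2 (two weeks post-baseline) for 4 weeks". The instruction page and the educational session come at the same visit, "both of which occur at two weeks post-baseline (Time 2 or T2".

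**Visits.** Table 1 heads its first column "Baseline (1 st meeting" and schedules the four outcome scales there and at weeks 2, 6 and 8. The compensation paragraph under Ethical Considerations counts baseline plus three follow-up collections. T2, where no writing has yet been done, is therefore a follow-up in the plan's own terms.

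**Analysis.** Data Analysis, Specific Aim 1, part b, contains three relevant statements:

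- Mean changes are "evaluated using regression models for longitudinal data (i.e., repeated measures analysis of variance"; no contrast or phase term is given.
- For Cohen's d, the "effect size will be computed by dividing the mean change by the standard deviation (SD) at the baseline"; the two visits behind the mean change are not named.
- For the FACT-G, "raw score changes from baseline to follow-up will be assessed to interpret the clinical significance of the change", by comparison with published minimal clinically important differences (MCID).

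**The concern.** Nothing is delivered between T1 and T2, so change over those two weeks cannot be an effect of writing. A FACT-G change measured from T1 includes it. Cohen's d may include it as well, depending on which visits are chosen later.

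Change before T2 is plausible. Patients enter "within 8 weeks of being informed of diagnosis (primary or recurrent", so they are at different points of early adjustment, and the plan itself notes that treatment modality may affect quality of life. The direction is not known: early adjustment would inflate the apparent effect and early decline would mask it.

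The primary aim is to produce effect sizes and from them a sample size for the main study. With one group and no control, the reference visit largely determines what the estimate means. T2 is the only measurement taken immediately before writing, and the analysis section gives it no role. Leaving the numerator of d undefined, with four visits and several outcomes, also leaves room to choose the visits after seeing the data.

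**Working it through.** **1. Timeline (Study Design; Table 1).** T1 = week 0, T2 = week 2, T3 = week 6, T4 = week 8. Writing runs from week 2 to week 6. The pre-writing interval is 2/6 = 33% of T1 to T3 and 2/8 = 25% of T1 to T4.

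**2. The plan's own figure.** The Study Population section gives a minimum of 50 for a paired one-sample comparison with effect size 0.4 to 0.5, α 0.05 and power 0.80. Sidedness is not stated; two-sided is assumed.

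- n = ((1.960 + 0.842)/0.4)² = 49.06, rounded up to 50. The exact t calculation gives 52.
- At 0.5, n = 31.4, rounded up to 32 (exact t: 34).

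The stated 50 reproduces at the lower end of the range, with no dropout allowance. The sample-size arithmetic is not the problem.

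**3. What drift does to each contrast.** The documents give neither a drift rate nor a between-visit correlation, so these are assumptions: n = 50, equal SDs (unit), equal correlation r between visits of 0.5 or 0.7, two-sided 5% paired t-test, positive change = improvement. For a mean change δ in SD units:

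- d_z = δ / √(2(1 − r)); the divisor is 1 at r = 0.5 and √0.6 = 0.775 at r = 0.7.
- Power comes from the noncentral t with 49 df and noncentrality d_z√50.
- δ = writing effect + drift × weeks, with 6 weeks for T1 to T3 and 4 weeks for T2 to T3.

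| Scenario | δ, T1–T3 | Significant (r = 0.5 / 0.7) | δ, T2–T3 | Significant (r = 0.5 / 0.7) |
|---|---|---|---|---|
| Drift +0.05/week, no writing effect | 0.05 × 6 = 0.30 | 55% / 77% | 0.05 × 4 = 0.20 | 28% / 43% |
| Drift +0.02/week, no writing effect | 0.12 | 13% / 19% | 0.08 | 9% / 11% |
| Drift −0.05/week, writing effect 0.4 | 0.4 − 0.30 = 0.10 | 11% / 15% | 0.4 − 0.20 = 0.20 | 28% / 43% |
| No drift, writing effect 0.4 | 0.40 | 79% / 95% | 0.40 | 79% / 95% |
| 0.2 SD change confined to T1–T2, no writing effect | 0.20 | 28% / 43% | 0 | 5% / 5% |

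Under steady drift, moving the reference to T2 removes 2 of 6 weeks, one third of the bias. The last row is the case most favourable to a T2 reference, and nothing in the documents supports it over the others.

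**4. Illustration for the main study.** Its design is not stated. Assume a paired single-group study, 80% power, a true effect of 0.4 SD and drift of +0.05 SD per week.

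| Reference for d | d used | N (r = 0.5 / 0.7) | Power at the true 0.4 SD |
|---|---|---|---|
| True effect | 0.40 | 52 / 32 | 81% / 81% |
| T2 | 0.40 + 0.20 = 0.60 | 24 / 16 | 47% / 49% |
| T1 | 0.40 + 0.30 = 0.70 | 19 / 12 | 38% / 37% |

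**5. Precision.** The 95% half-width is t(0.975, 49) × √(2(1 − r)/50) = 2.010 × √(2(1 − r)/50), which is 0.28 SD at r = 0.5 and 0.22 SD at r = 0.7. Under equal correlation it is the same for T3 − T1 and T3 − T2, so the later reference loses no precision.

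**The case against.** The strongest reply is that only one of the three analyses states a T1 reference, and that one is an interpretive aid for the FACT-G which is not said to size anything. For d and the repeated-measures model the plan is silent, not wrong. The design is called a time series, has two measurements before writing, and can yield T2 − T1 and T3 − T2 from data already planned. The paragraph on treatment modality mentions intervention effect and change over time as separate things. The timeline figure cannot be seen and might mark the phases.

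This stands as a limit on the claim. For d the fault is an undefined numerator, and harm to the main study is possible, not certain. It does not remove the point: no readable text sets T2 as the reference or identifies T2 − T1 as change without intervention, and the one reference that is stated is T1.

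A second reply is that most of the bias under steady drift comes from having no control group, and that a T2 reference leaves two thirds of it. That is correct. The drift rates and correlations are assumed, and the main-study figures also assume a design the documents do not give, so they show direction and scale only. Equal precision likewise depends on equal correlation.

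A third reply concerns the order of procedures at T2. The FACIT-Sp-12, FACT-G and HADS ask about the past week, so T2 answers mostly describe time before the session in either order. Only the self-esteem scale has no recall period. Fixing the order is therefore a minor safeguard.

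**Conclusion.** The concern holds. For the raw FACT-G change the reference is wrong as written if the result is read as an effect of writing: one third of the T1 to T3 interval precedes the intervention. For Cohen's d and the repeated-measures model the reference is open, and naming T2 would be an improvement at no cost.

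The size cannot be fixed from the documents. Over the assumed drift of 0.02 to 0.05 SD per week, the two pre-writing weeks add 0.04 to 0.10 SD to a T1-based effect in either direction (2 × 0.02 and 2 × 0.05). At the upper value with no writing effect, the chance of a significant result is 55% to 77% from T1 against 28% to 43% from T2. The plan should be changed, because the effect size is the main product of the study. The change reduces the bias and does not remove it.

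**What to change.** In Data Analysis, Specific Aim 1, part b:

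1. Define the intervention contrast as T3 minus T2, estimated from the four-visit model, with T4 minus T2 as persistence.
2. Compute the mean change in Cohen's d and the raw change compared with the MCID from T2. Keep the T1 SD as the denominator, as the plan already states.
3. Report T2 minus T1 beside these on the same scale, labelled as the no-intervention change.
4. State that the T2 questionnaires are completed before the T2 instruction session.
5. State that change continuing after T2 cannot be separated from the writing effect without a control group, and carry this caution into the main-study sample size.

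The cost is analysis wording and one sentence on the order of procedures at T2. All four visits are already scheduled, so no extra data or participants are needed.

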the FACT-G. Raw scores at the baseline and follow-up will be compared with the norm reference or thresholds for clinical consideration, if available in the literature.

Although psychological adaptation seems to be fundamentally independent from diagnostic group (Cassileth et al., 1984), treatment modality may exert an effect on quality of life outcomes (Oates et al., 2014). The type of anticancer treatment patient received will be collected from the patient's chart; analysis of intervention effect and change over time will take treatment modality (as well as the diagnostic groups) into consideration (in subgroup or post-hoc exploratory analysis).

Specific Aim 2. Test the validity of the 12-item functional assessment of chronic illness therapy- spiritual well-being scale (FACIT-Sp-12), in its current and revised forms.

To verify the understanding of the updated Factor items in the revised FACIT-Sp-12 and compare with the original scale, patients will be asked about their interpretation of the items in the Faith factor for both the original and revised scales (Schuman, 1966).

Cronbach's coefficient alpha will be computed to examine internal consistency reliability for both the revised and the original FACIT-Sp-12. The homogeneity of the total scale and three factors of Meaning, Peace and Faith will be examined by the mean inter-item correlations, item-total correlations and item-rest correlations for both the original and revised FACIT-Sp-12. Construct validity will be explored by assessing the associations of the FACIT-Sp-12 (original and revised) with QoL (global and total FACT-G), self-esteem, and psychological distress (anxiety and depression).

The threshold for the clinically important difference for the FACIT-Sp-12 at the scale and factor levels has not yet been reported in the literature. In this study, the MCIDs for scores of the scales and subscales from both the original and the revised FACIT-Sp-12 will be estimated using the criterion of global ratings of changes (GRC) on the five-point response categories (Cella et al., 2002).

In addition, to examine whether the associations between the individual items and any sample characteristic may differ, which could suggest *item bias* or differential item functioning (Groenvold, Bjorner, Klee, & Kreiner, 1995), the validities of the FACIT-Sp-12 concerning the Faith factor will be further examined with the differential item functioning analysis in both the original and the revised FACIT-Sp-12.

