Below is a list of statements that other people with your illness have said are important. **Please circle or mark one number per line to indicate your response as it applies to the past 7 days.**

PHYSICAL WELL-BEING

		Not at all	A little bit	Some- what	Quite a bit	Very much
GP1	I have a lack of energy	0	1	2	3	4
GP2	I have nausea	0	1	2	3	4
GP3	Because of my physical condition, I have trouble meeting the needs of my family	0	1	2	3	4
GP4	I have pain	0	1	2	3	4
GP5	I am bothered by side effects of treatment	0	1	2	3	4
GP6	I feel ill	0	1	2	3	4
GP7	I am forced to spend time in bed	0	1	2	3	4

SOCIAL/FAMILY WELL-BEING

		Not at all	A little bit	Some- what	Quite a bit	Very much
GS1	I feel close to my friends	0	1	2	3	4
GS2	I get emotional support from my family	0	1	2	3	4
GS3	I get support from my friends	0	1	2	3	4
GS4	My family has accepted my illness	0	1	2	3	4
GS5	I am satisfied with family communication about my illness	0	1	2	3	4
GS6	I feel close to my partner (or the person who is my main support)	0	1	2	3	4
Q1	Regardless of your current level of sexual activity, please answer the following question. If you prefer not to answer it, please mark this box  and go to the next section.					
GS7	I am satisfied with my sex life	0	1	2	3	4

FACT-G

Please circle or mark one number per line to indicate your response as it applies to the past 7 days.

EMOTIONAL WELL-BEING

		Not at all	A little bit	Some- what	Quite a bit	Very much
--	--	-----------------------	-------------------------	-----------------------	------------------------	----------------------

GE1	I feel sad	0	1	2	3	4
GE2	I am satisfied with how I am coping with my illness.....	0	1	2	3	4
GE3	I am losing hope in the fight against my illness.....	0	1	2	3	4
GE4	I feel nervous.....	0	1	2	3	4
GE5	I worry about dying.....	0	1	2	3	4
GE6	I worry that my condition will get worse	0	1	2	3	4

FUNCTIONAL WELL-BEING

		Not at all	A little bit	Some- what	Quite a bit	Very much
--	--	-----------------------	-------------------------	-----------------------	------------------------	----------------------

GF1	I am able to work (include work at home)	0	1	2	3	4
GF2	My work (include work at home) is fulfilling.....	0	1	2	3	4
GF3	I am able to enjoy life.....	0	1	2	3	4
GF4	I have accepted my illness.....	0	1	2	3	4
GF5	I am sleeping well	0	1	2	3	4
GF6	I am enjoying the things I usually do for fun	0	1	2	3	4
GF7	I am content with the quality of my life right now.....	0	1	2	3	4

ID #
Visit Date:

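### The plan specifies no timing for anticancer treatment and uses modality only in subgroup or post-hoc analysis, so treatment started or stopped during follow-up enters the FACT-G effect size

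*Combined protocol and SAP*

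**What the plan says.** **Design.** Under Study Design and Procedures, "A single group time series study design will be employed". Writing runs "starting from Time 2 (two weeks post-baseline) for 4 weeks". Table 1 schedules FACT-G at baseline and at weeks 2, 6 and 8.

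**Who enters.** The first inclusion criterion is "within 8 weeks of being informed of diagnosis (primary or recurrent").

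**What is recorded about treatment.** The Measures section (Checklist of Intervention Implementation) takes medical conditions and cancer treatments from the medical record. Data Analysis, Specific Aim 1b, says "The type of anticancer treatment patient received will be collected" from the chart. Neither mentions start dates, stop dates or changes of therapy. Table 1 has a row for disease progress at weeks 2, 6 and 8 but none for treatment.

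**How it is used.** Aim 1b accepts that modality may affect quality of life. When the effect of writing and the course over visits are analysed, the intention is to "take treatment modality (as well as the diagnostic groups) into consideration (in subgroup or post-hoc exploratory analysis"). The only covariates named for the longitudinal model are psychosocial and supportive care. Disease progression and perceived threat are exploratory moderators.

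**What is reported.** The effect size is mean change over baseline SD. Raw FACT-G change from baseline to follow-up is also compared with a published minimal important difference.

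**The concern.** With no control group, anything else that changes over the same weeks becomes part of the mean change. Patients can be anywhere from 0 to 8 weeks past hearing the diagnosis at entry, and up to 8 + 8 = 16 weeks past it at the last visit. Some can be expected to start, stop or change anticancer treatment in that time.

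FACT-G is exposed to this by its content. Its physical scale includes nausea, energy, and an item reading "I am bothered by side effects of treatment".

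The planned safeguard is grouping by modality, which does not address timing. Two patients on the same treatment, one already established on it at baseline and one starting it at week 3, fall in the same group yet may have FACT-G courses that run in opposite directions.

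The primary aim is to calculate effect sizes and size the main study. A FACT-G effect size that is partly a treatment effect would carry over into that calculation.

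**Working it through.** **1. The plan's own figure.** Study Population says "the total number of subjects to be enrolled will be a minimum of 50", chosen "based on an estimated effect size of 0.4-0.5 to test differences between paired observations in one sample, with α 0.05 and power 0.80". For a paired comparison, n = ((z for two-sided 0.05 + z for power 0.80) / d)² = ((1.960 + 0.842) / d)².

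- d = 0.4: 7.849 / 0.16 = 49.1, so 50 (52 by the exact t calculation).
- d = 0.5: 7.849 / 0.25 = 31.4, so 32 (34 by exact t).

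The figure of 50 reproduces at the lower effect size, two-sided, with no dropout allowance. It covers one whole-sample comparison, and the present point does not change it.

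**2. How much of FACT-G is exposed.** Items are scored 0-4. Physical well-being has 7 of 27 items, or 28 of 108 points. With functional well-being it is 14 of 27 items, or 14 × 4 = 56 of 27 × 4 = 108 points.

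**3. Illustrative shift from treatment starts.** The documents give none of these inputs, so all three are assumptions: 20-40% of patients start treatment between baseline and the follow-up visit; FACT-G falls 4-8 points in those who start; baseline SD is 15-18.

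Shift = share starting × mean fall / baseline SD.

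| | Share | Fall | Mean shift | SD | Shift in SD |
|---|---|---|---|---|---|
| Small end | 0.20 | 4 | -0.8 | 18 | -0.04 |
| Large end | 0.40 | 8 | -3.2 | 15 | -0.21 |

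Patients whose treatment ends, or relieves symptoms, would move the mean the other way. That part is not quantified, so the net sign is unknown.

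**4. What it could do to the main study's size.** Take a true d of 0.4, the rounded shifts above and the same paired formula. This is an illustration only. The plan scales d by the baseline SD, while the paired formula uses the SD of differences. The two agree only if visit SDs are equal and the between-visit correlation is about 0.5.

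- Masked by 0.04: d = 0.36, n = 7.849 / 0.1296, so 61.
- Masked by 0.21: d = 0.19, n = 7.849 / 0.0361, so 218.
- Inflated by 0.04: d = 0.44, n = 7.849 / 0.1936, so 41.
- Inflated by 0.21: d = 0.61, n = 7.849 / 0.3721, so 22.

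The inflated cases mirror the masked ones and have no separate calculation behind them.

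**5. What it could do to the pilot's test.** Assume 40% start treatment and each shifts by 0.5 SD, so the bias is 0.4 × 0.5 = 0.20. With no writing effect and n = 50, the chance of a significant change (two-sided 0.05) is 27% if the between-visit correlation is 0.5, and 40% if it is 0.7.

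**6. Whether modality subgroups can help.** They do not carry timing. They are also small: at d = 0.4, power is 0.48 with 25 patients and 0.34 with 17 (subgroup sizes assumed).

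**The case against.** The strongest reply is that this is a declared exploratory pilot. Its authors recognise that treatment affects quality of life and assign it to exploratory analysis, and the root limitation is the single-group design, which no covariate repairs. Each FACT-G subscale is analysed separately, so a shift confined to physical well-being would be visible. Self-esteem, spiritual well-being, anxiety and depression are separate outcomes. There is also a two-week pre-writing interval.

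Much of this stands, and it limits the point to FACT-G and to a supporting analysis. It does not dispose of it. Seeing a subscale move does not show whether writing or treatment moved it. The plan names no contrast that uses the pre-writing interval, and that interval could not account for treatment begun after week 2.

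Some stronger readings are tempting but unsupported:

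- **That only treatment type is recorded.** The Measures section is broader, and no abstraction form is shown. What can be said is that timing is not specified.
- **That the trial's estimate is the change from week 2 to week 6.** No section names that contrast. Aim 1b refers to change from baseline to follow-up, a longer window with more time for treatment to start.
- **That the main model already adjusts for disease progression.** It is an exploratory moderator.
- **That the shift is known to be about half the planned effect.** That takes the large end of three outside assumptions, ignores offsetting changes, and compares it with an effect of 0.4-0.5 that the plan does not tie to FACT-G.
- **That FACT-G is affected most.** This is a reasonable inference from item content, but the documents give no sizes.

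**Conclusion.** The point holds in limited form. No section plans treatment dates, visit-level treatment status, or anticancer treatment as a covariate in the longitudinal model. With no control group, change caused by starting or stopping treatment during follow-up is therefore part of the FACT-G mean change and of the effect size passed to the main study. Grouping by modality cannot separate it.

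The size is not known from the documents and the direction can be either way. Under the stated assumptions, starts alone give about -0.04 to -0.21 baseline SD, which ranges from negligible to enough to alter a sample size seriously. The omission itself is established from the text; the magnitude is only illustrative. The change should be made because it is cheap and bears on the primary aim. It does not invalidate the pilot or its minimum of 50.

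**What to change.** **Data.** During the chart abstraction already planned, also record anticancer treatment start and stop dates. From these, code one simple status per visit: either on or off treatment, or started or stopped since the previous visit (yes/no). On/off has the advantage of being defined at all four visits, baseline included. A finer set of categories would be too sparse with about 50 patients.

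**Analysis.** Pre-specify a sensitivity analysis for FACT-G total, its subscales and GF7 that adds this status as a time-varying covariate to the longitudinal model. Report the model-estimated change from baseline divided by the baseline SD, with and without the covariate. Modality stays in the exploratory subgroup analysis.

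**Reporting.** State that the adjustment reduces confounding but does not remove it where treatment starts coincide with the writing weeks, because status and visit then move together. Note also that a single status pools modalities whose effects may differ. If the two FACT-G effect sizes differ materially, carry both into the main-study sample size calculation.

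**Cost.** A few date fields, one model term, a short addition to the analysis section, and a somewhat wider interval in the adjusted analysis. No visits or patient questionnaires are added.
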